Grade 2 mucositis	If the toxicity is tolerable to the patient, maintain the same dose. If the toxicity is intolerable to patient, interrupt RAD001 and pasireotide until recovery to grade ≤ 1 . Then reintroduce RAD001 and pasireotide at one lower dose level. See Management of stomatitis/oral Mucositis/mouth ulcers for further details.
Grade 3 (except hyperlipidemia and hyperglycemia and mucositis and pneumonitis)	Interrupt RAD001 and pasireotide until recovery to grade ≤ 1 . Then reintroduce RAD001 and pasireotide at one lower dose level. If the same toxicity recurs at CTC grade ≥ 3 SOM230 and RAD001 will be discontinued.
Grade 3 hyperlipidemia	Grade 3 hyperlipidemia (hypercholesterolemia and/or hypertriglyceridemia) should be managed using medical therapies, see Management Guidelines for Hyperlipidemia and Hyperglycemia. Dose reduction of RAD001 and pasireotide can be considered but is not required.
Grade 3 hyperglycemia	Grade 3 hyperglycemia should be managed using medical therapies, see Management Guidelines for Hyperlipidemia and Hyperglycemia. Dose reduction of RAD001 or pasireotide can be considered but is not required.
Grade 3 mucositis	For Grade 3 mucositis, interrupt RAD001 until recovery to grade ≤ 1 . Then reintroduce RAD001 and pasireotide at one lower dose level See Management of stomatitis/oral Mucositis/mouth ulcers for further details.
Grade 3 pneumonitis	Please refer to Table 6-5
Grade 4	Discontinue pasireotide and RAD001.

Any non-hematological toxicity requiring interruption for > 3 weeks	Discontinue pasireotide and RAD001.
---------------------------------------------------------------------	-------------------------------------

Table 6-4 Criteria for dose-modification in case of suspected SOM230 and RAD001 for hematologic toxicity

Toxicity	Actions
Hematological toxicity	
Grade 2 Thrombocytopenia (platelets $<75, \geq 50 \times 10^9/L$)	Interrupt RAD001 until recovery to grade ≤ 1 ($>75 \times 10^9/L$). Then reintroduce RAD001 at initial dose. If thrombocytopenia again returns to grade 2, interrupt RAD001 until recovery to grade ≤ 1 . Then reintroduce RAD001 at the lower dose level.
Grade 3 Thrombocytopenia (platelets $<50, \geq 25 \times 10^9/L$)	Interrupt RAD001 until recovery to grade ≤ 1 (platelets $\geq 75 \times 10^9/L$). Then resume RAD001 at one dose level lower. If grade 3 thrombocytopenia recurs, discontinue RAD001.
Grade 4 Thrombocytopenia (platelets $< 25 \times 10^9/L$)	Discontinue RAD001.

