Grade 3 Neutropenia (neutrophils $<1, \geq 0.5 \times 10^9/L$)	Interrupt RAD001 until recovery to grade ≤ 1 (neutrophils $\geq 1.5 \times 10^9/L$). Then resume RAD001 at the initial dose. If ANC again returns to Grade 3, hold RAD001 until the ANC $\geq 1.5 \times 10^9/L$. Then resume RAD001 dosing at the lower dose level. Discontinue patient from study therapy for a third episode of grade 3 neutropenia. If clinically indicated, patient with prolonged neutropenia may be treated with growth factors.
Grade 4 Neutropenia (neutrophils $< 0.5 \times 10^9/L$)	Interrupt RAD001 until recovery to grade 1 (neutrophils $\geq 1.5 \times 10^9/L$). Then resume RAD001 at the lower dose level. If grade 3 or grade 4 neutropenia occurs despite this dose reduction, discontinue RAD001. If clinically indicated, patient with prolonged neutropenia may be treated with growth factors.
Grade 3 febrile neutropenia (not life-threatening)	Interrupt RAD001 until resolution of fever and neutropenia to grade ≤ 1 . Hold further RAD001 until the ANC $\geq 1,500/mm^3$ and fever has resolved. Then resume RAD001 at the lower dose level. If febrile neutropenia recurs, discontinue RAD001. If clinically indicated, patient with prolonged neutropenia may be treated with growth factors.
Grade 4 febrile neutropenia (life-threatening)	Discontinue RAD001.
Any hematological or non-hematological toxicity requiring interruption for ≥ 3 weeks	Discontinue RAD001

*Grade 3 hyperlipidemia (hypercholesterolemia and/or hypertriglyceridemia) should be managed using medical therapies (see Sec. 3.2.5.2).

Management of non-infectious pneumonitis

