6.9 Study drug discontinuation

Patients experiencing unacceptable toxicity (AE grade 3 or higher) that the investigator considers directly attributable to the study drug should have their dose adjusted as per dose modification guidelines in Table 6-2. If a patient has already decreased 2 dose levels, no further dose reduction is permitted, and the patient will be permanently discontinued from treatment. A delay of more than 21 days in resuming study drug due to treatment-emergent adverse event will result in the withdrawal of the patient from the study (non-treatment related delay of more than 21 days but no more than 28 consecutive days may be allowed to resume therapy after discussion with the overall PI). Patient so withdrawn should undergo the required end of study procedures follow-up post treatment discontinuation.

Premature patient withdrawal/End of treatment

Patients **may** voluntarily withdraw from the study or be dropped from it at the discretion of the investigator at any time. Patients may be withdrawn from the study if any of the following occur:

- Disease progression or lack of efficacy
- Uncontrolled diabetes mellitus (DM)
- Pregnancy
- Adverse event(s)
- Abnormal laboratory value(s)
- Abnormal test procedure result(s)

QT-related discontinuation criteria

- Confirmed QTcF >480msec and discontinuation recommended by a cardiologist
- New occurrence of clinically significant/symptomatic bradycardia
- Increased risk of QT prolongation by use of QT prolonging medication
- Hypokalemia (<3.5 mmol/L) or hypomagnesaemia (<0.7 mmol/L) confirmed by repeat testing that is either a new finding or accompanied by vomiting or diarrhea and not corrected by treatment
- Protocol violation
- Subject withdrew consent
- Lost to follow-up
- Administrative problems
- Death
- Disease progression
- Treatment duration completed as per protocol

7 Visit schedule and assessments

Table 7-1 lists all of the assessments and indicates the visits at which they are to be performed with an “X”. All data obtained from these assessments must be supported in the patient’s source documentation. To accommodate scheduling challenges, the required assessments may be performed within +/- 2 days of the specified scheduled dates.

Hepatitis Screening

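### For patients on both drugs, the rules for a prolonged toxicity hold conflict on whether both drugs stop, everolimus alone stops, or the patient leaves the study

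*Combined protocol and SAP*

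**What the plan says.** The rules that bear on a long hold, or on which drug is stopped, are these.

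- **Section 6.7, Table 6-3, last row.** The trigger is "Any non-hematological toxicity requiring interruption for > 3 weeks" and the action is "Discontinue pasireotide and RAD001".
- **Section 6.7, Table 6-4, last row.** The trigger is "Any hematological or non-hematological toxicity requiring interruption for" 3 weeks or longer. The action names RAD001 only.
- **Section 6.7, follow-up for toxicities.** A patient whose SOM230 and RAD001 dosing is delayed beyond 21 days, counted from the day the next dose was due, comes off the study.
- **Section 6.9.** This rule ends study participation: "A delay of more than 21 days in resuming study drug due to treatment-emergent adverse event will result in the withdrawal of the patient from" … Only a delay unrelated to treatment may run on to 28 days, after discussion with the overall principal investigator.
- **Table 6-3, mucositis rows.** Intolerable grade 2 mucositis interrupts both drugs. The grade 3 row reads "For Grade 3 mucositis, interrupt RAD001 until recovery to grade" 1 or lower, and then brings back both RAD001 and pasireotide at a lower level.
- **Table 6-4, neutropenia rows.** The grade 3 row says "Discontinue patient from study therapy for a third episode of grade 3 neutropenia". The grade 4 row says "If grade 3 or grade 4 neutropenia occurs despite this dose reduction, discontinue RAD001".

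Section 6.3 defines Arm C as the two drugs given together, and Arms A1 and B1 as patients switched to the combination. It has no rule for continuing on one drug.

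**The concern.** For a patient on one drug, most of these rules come to the same thing. For a patient on two drugs they do not: the same event can stop both drugs, stop RAD001 with nothing said about pasireotide, or end study participation. Sites that open different tables could handle the next monthly injection differently.

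The analysis is exposed as well. Section 7.4 treats a patient who stops for drug-related toxicity before a restaging scan as inevaluable and replaces that patient. A patient who completes two cycles is evaluable. The stopping rule a site follows can therefore decide who is in the Arm C response denominator. TTF is a secondary objective in Section 3.2, but the plan does not define it, so it is open whether stopping one drug of two counts as failure.

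**Working it through.** No figure in the plan needs reproducing. The check sets the triggers side by side.

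**Step 1: non-hematological toxicity, both drugs held.** Three weeks is 3 × 7 = 21 days.

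| Length of hold | Table 6-3, last row (> 21 days) | Table 6-4, last row (≥ 21 days) | Section 6.9 (> 21 days) |
|---|---|---|---|
| 20 days | not triggered | not triggered | not triggered |
| 21 days | not triggered | RAD001 stopped | not triggered |
| 22 days | both drugs stopped | RAD001 stopped | off study |

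At exactly 21 days only Table 6-4 acts. From 22 days there are three different stated outcomes. A split between hematological and non-hematological toxicity does not explain this, because the Table 6-4 row names both classes. The 28-day allowance in Section 6.9 does not help, because it is limited to delays unrelated to treatment.

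**Step 2: hematological toxicity.** Table 6-3 does not apply. At 22 days Table 6-4 stops RAD001 and Section 6.9 withdraws the patient, so two rules still differ.

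**Step 3: the clock in the follow-up text of Section 6.7.** This rule counts from the next scheduled dose and refers to both drugs. Suppose both drugs are held from day 10 of cycle 1. On day 32 everolimus has been interrupted for 32 − 10 = 22 days. The next pasireotide injection was due on day 29, so it is 32 − 29 = 3 days late, and its delay first exceeds 21 days on day 29 + 22 = 51. The interruption rules and this rule can be 51 − 32 = 19 days apart for one event.

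**Step 4: mucositis.** The grade 3 row interrupts one drug and reintroduces two, so it contradicts itself. It also differs from the grade 2 row, which interrupts both.

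**Step 5: link to evaluability.** A cycle is 4 weeks and the first restaging is at the end of cycle 2, day 2 × 28 = 56. A hold that starts on day s reaches 22 days on day s + 22. This falls before day 56 when s is below 56 − 22 = 34. For such a hold, stopping all treatment makes the patient inevaluable and replaced under Section 7.4. If pasireotide were continued, the patient could reach the scan and be counted.

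**Step 6: how many.** The documents give no rate for the combination. Section 6.7 quotes 7% permanent discontinuation for adverse reactions on everolimus alone in renal cell carcinoma. Section 5 plans 30 patients per arm, so 0.07 × 30 = 2.1, about 2 patients, if that rate is assumed for Arm C.

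**The case against.** The strongest reply is that the rules are cumulative. Stopping RAD001 does not say that pasireotide goes on, Arm C is defined as both drugs, and withdrawal under Section 6.9 would satisfy every row at once beyond 21 days. That reading is possible, and a reader who infers that the protocol allows pasireotide alone goes too far: this is only implied by Table 6-4 naming RAD001 alone, and nothing expressly permits it. But the protocol does not state that the rules are cumulative or which one governs. The reading would also leave the 21-day cut-off mismatch and the mucositis row unresolved.

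Three further inferences are tempting and not supported.

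- **That the neutropenia rows contradict each other, with the milder course stopping more.** They cover different histories: a third grade 3 episode, and a recurrence after a grade 4 episode despite dose reduction. The broader term in the grade 3 row may be loose wording for RAD001. It is a minor point of consistency.
- **That about 12 of 30 Arm C patients are affected.** This comes from the 39% of everolimus patients with grade 3 or 4 reactions (0.39 × 30 = 11.7). That figure measures neither stopping nor three-week holds, and it omits grade 2 events, so it is not an upper limit.
- **That the response decision for Arm C is shown to change.** The denominator can change; no effect on the threshold of 3 responses in 28 has been demonstrated.

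It is also fair to say that Section 4 has a separate rule for switchers. They may continue only if the first two combination cycles pass without grade 4 or higher hematologic or grade 3 or higher non-hematologic toxicity. That narrows the problem in Arms A1 and B1. The missing TTF definition is a gap in its own right, which these tables make more visible.

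**Conclusion.** The concern holds for prolonged holds and for grade 3 mucositis. Read as complete instructions, the last rows of Tables 6-3 and 6-4 and Section 6.9 cannot all be followed for a patient on both drugs with a non-hematological hold beyond 21 days. For hematological toxicity, Table 6-4 and Section 6.9 differ. The follow-up text of Section 6.7 adds a second clock. The neutropenia wording is a minor addition.

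The number affected is unknown. About 2 of 30 Arm C patients rests on carrying the single-agent everolimus discontinuation rate over to the combination, which may be too low. The contradiction does not depend on that number. The effect on the response denominator assumes that the evaluability and replacement rule in Section 7.4 is the one applied.

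**What to change.** The sponsor should reconcile the following, and the clinical choice in each is the sponsor's:

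- the last rows of Tables 6-3 and 6-4 with the follow-up text of Section 6.7 and with Section 6.9, giving one cut-off, one clock and one stated outcome;
- the grade 2 and grade 3 mucositis rows of Table 6-3;
- the stopping term used in the neutropenia rows of Table 6-4.

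The reconciled text should say which drug is stopped and whether a patient on two drugs stays on study. The statistical section should define TTF and state whether stopping one drug in Arm C is a TTF event.

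The cost is a protocol amendment to two tables and two paragraphs, plus a short definition. It adds no patients or procedures. Little new data capture should be needed: Section 6.7 already requires dose changes to be recorded, and the Appendix C diary has separate entries for the length of interruption of each drug.

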- Referral to a diabetes specialist for evaluation and appropriate management
- Provided information and receive teaching on diabetes disease management
- Monitoring of blood glucose by fingerstick twice daily (fasting morning blood glucose and 2-hour post-meal) if not already done. Patients, who monitor blood glucose should keep a diary of their glucose values and present the collected data to their physician/ diabetes specialist for evaluation and appropriate management.

Management Guidelines for ECG Monitoring for Prolonged QT

ECG frequency for SOM230 LAR studies:

ECG monitoring is recommended at the following time points:

- Baseline (before SOM230 LAR injection)
- 21 days after 1st SOM230 LAR injection
- 21 days after 3rd SOM230 LAR injection
- Cycle 6 (before SOM230 LAR injection)
- Every 3 cycles after Cycle 6
- ECG should be done at any time when clinically indicated

ECG procedures in the event of prolonged QTc

- If at any visit a QTcF > 480 msec is observed, the following steps need to be taken:
 - A cardiology consultation must be sought as soon as practicable but within 7 days of the initial abnormal ECG and the cardiologist must re-evaluate the ECG (this can be done by the central cardiologist if the trial has one).
 - If a QTcF > 480 msec is NOT confirmed, no further action needs to be taken.

- If a QTcF>480msec is confirmed, a cardiologist must perform a thorough examination (such as reviewing baseline ECG, concurrent medications and performing a cardiovascular examination (including at least a cardiac auscultation)) to assess the patient for cardiovascular risk factors.
 - If based upon the assessment by the cardiologist, the investigator considers that there is an acute cardiovascular safety risk and that the patient should not continue with study medication, the patient needs to be discontinued immediately (discontinuation criteria to be followed).
 - If following the examination by the cardiologist, the investigator considers that there is not an acute cardiovascular safety risk and that the patient could continue to receive study medication, a Holter ECG (24hr) must be recorded soon as practicable but within 7 days after the initial abnormal ECG or at the next SOM230 LAR injection. The Holter-ECG must be started 30min prior to an injection of study medication.

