 - The results of the ECGs, cardiac examination, Holter-ECGs and the recommendation by the cardiologist must be evaluated by the investigator to determine whether the patient should continue in the trial or not (discontinuation criteria to be followed).
- **C_{max} drug concentration visit:** If at a Day 21 visit (day 21 after any injection of Pasireotide/Octreotide LAR) a C_{max} QTcF>480 msec is observed for the first time for a patient at a given dose level, the following steps need to be taken:
 - A cardiology consultation as described in the preceding section must be sought as soon as practicable but within 7 days after the initial abnormal ECG and prior to the next Pasireotide/Octreotide LAR injection.
 - All steps described in the preceding section must be followed, however if a Holter ECG is required, a 24hour Holter ECG must be recorded when the patient receives the next scheduled Pasireotide/ Octreotide LAR injection. The Holter ECG should be started 30min prior to the injection.
- **Trough concentration visit e.g. day 1 of a new cycle:** If at any visit a trough level QTcF>480 msec is observed for the first time for a patient at a given dose level, the following steps need to be taken:
 - A cardiology consultation as described in the preceding section must be sought as soon as practicable but within 7 days after the initial abnormal ECG and prior to the next Pasireotide/Octreotide LAR injection.
 - All steps described in the preceding section must be followed; however if a Holter-ECG is required, a 24hour Holter-ECG must be recorded and evaluated prior to the next injection of Pasireotide/Octreotide LAR. The Pasireotide/Octreotide injection must be postponed until the Holter-ECG results are available with a maximal permissible delay of 7 days. If the outcome of the cardiac evaluation is that the patient may receive a further dose of Pasireotide/Octreotide LAR, then a second 24hr Holter-ECG must be done on the day of the LAR injection.

- This Holter ECG should be started 30min prior to the injection.

Table 6-8a: Guidelines for dose modification for QT prolongation while on SOM230

Adverse event	Action
*Grade ≤ 2	No study drug adjustments

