*Grade ≥ 3 and judged as at least possibly drug related	
 · Further injections should be held for at least 7 days and until toxicity improves to \leq Grade 1. · If toxicity improves to grade ≤ 1 within 7 days, no dose reduction is required. · If toxicity improves to grade ≤ 1 in 8-14 days, resume treatment with a single dose level reduction. · If toxicity improves to grade ≤ 1 in 15-28 days, resume treatment with two dose level reductions. · If toxicity fails to improve to grade ≤ 1 within 28 days, study treatment must be discontinued unless there is clear evidence of therapeutic benefit from the study regimen, in which case continued treatment is left to the discretion of the Overall Principal Investigator. · If any toxicity recurs at CTCAE grade ≥ 3, treatment must be discontinued.
QTc CTC grade 1 (≤ 480 msec)	
 · No study drug adjustments
QTc CTC grade 2 (> 480 or ≤ 500 msec) either drug related or drug unrelated	Patient is to be referred to a cardiologist for evaluation and appropriate management, and the patient can remain in the study 
 · Patient's study drug dose will be reduced to 1 dose level down
QTc CTC grade ≥ 3 (> 500 msec)	Discontinue study drug Follow patient for safety ^A

SOM230 Management Guidelines for Suspected Hepatic Toxicity

In case of suspected SOM230-related hepatic injury manifesting as abnormal LFTs, the following steps should be followed within 72 hours of awareness of abnormal liver function tests:

- Liver-directed medical history and physical examination (i.e. assess occupational hazards, concomitant medications including OTC meds, intercurrent illness, etc)
- Liver chemistry tests: ALT, AST, total bilirubin, (fractionate to direct/indirect bilirubin if total bilirubin is $> 2.0x$ ULN), Alb, PT (INR), ALP, and GGT
- Hepatitis screen:
 - anti-HAV, IgM (to confirm acute hepatitis A)
 - HbsAg, Anti-HBc
 - anti-HCV (if positive, PCR viral load should be assessed),
 - Anti-HEV
 - ANA antibodies, anti-smooth muscle anti-bodies, CMV, EBV
- Perform abdominal ultrasound (liver and biliary tree)

Liver chemistry tests should be monitored every 3-4 days until resolution or return to baseline status.

- For ALT or AST $> 5x$ ULN and $\leq 8x$ ULN:
 - Study medication should be temporarily interrupted and liver chemistry tests monitored every 3-4 days until resolution or return to baseline

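### As its visible text stands, Table 6-8a gives two incompatible pasireotide actions for the same QTc event and does not say which row governs

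*Combined protocol and SAP*

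**What the plan says.** The title of Table 6-8a (section 6.7) is "Guidelines for dose modification for QT prolongation while on SOM230". The table has two sets of rows.

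Starred rows, by grade:
- Grade ≤2: "No study drug adjustments".
- Grade ≥3, possibly due to the drug: hold injections until grade ≤1. The dose is unchanged after recovery within 7 days and one level lower after 8 to 14 days. For slower recovery the instruction is "in 15-28 days, resume treatment with two dose level reductions". Without recovery by day 28 treatment stops, unless there is clear benefit, "in which case continued treatment is left to the discretion of the Overall Principal Investigator".

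QTc rows, by msec:
- Grade 1 (up to 480): no change.
- Grade 2 (above 480, up to 500), "either drug related or drug unrelated": cardiology referral, and the "study drug dose will be reduced to 1 dose level down".
- Grade ≥3 (above 500): "Discontinue study drug Follow patient for safety". There is no condition on relatedness and no path to resume.

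No note explaining the asterisk is visible, and no sentence ranks the two sets.

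Other places bear on the same event:
- The ECG procedures in section 6.7 apply to any QTcF above 480 msec: "A cardiology consultation must be sought as soon as practicable but within 7 days of the initial abnormal ECG". The cardiologist re-reads the ECG, and an unconfirmed finding needs no further action.
- Section 6.9, under QT-related discontinuation criteria, lists confirmed QTcF above 480 msec together with a cardiologist's recommendation to stop. The list gives reasons for which a patient may be withdrawn. It has no entry for 500 msec.
- Table 6-3 covers non-hematologic toxicity in general. After grade 3 recovery both drugs restart one level lower; at grade 4 both stop. Its grade 3 exceptions do not include QT.

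**The concern.** A site that sees a drug-related QTc above 500 msec turns to the table written for that event and finds one row that allows another injection after recovery and another that ends treatment. Each could be cited as protocol text. The drug is a depot given every 4 weeks, so the decision to inject again cannot be reversed quickly. Arms B and C receive it from the start, and Arms A1 and B1 receive it in the combination after crossover, at several centers. The stake is patient safety and uniform handling across sites. It does not touch the efficacy analysis.

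**Working it through.** The plan states no figure to reproduce and gives no QTc event rate for pasireotide. The check sets the rules side by side.

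**Inputs.** Table 6-2 gives pasireotide levels of 60, 40 and 20 mg, so a patient starting at level 0 and reduced by k levels receives 60 − 20k mg.
- Starred grade ≥3 row: recovery within 7 days, k = 0, 60 mg; in 8–14 days, k = 1, 60 − 20 = 40 mg; in 15–28 days, k = 2, 60 − 40 = 20 mg.
- QTc grade 2 row: k = 1, 40 mg.
- Table 6-3, general grade 3 row: k = 1, 40 mg, whatever the recovery time within its 3-week interruption limit.

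**Reading 1: the starred rows cover QTc, as the table title suggests.**

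| Event | Starred row | QTc row |
|---|---|---|
| QTc 490 msec | 60 mg | 40 mg |
| QTc 510 msec, possibly drug related, recovery within 7 days | hold, then 60 mg | discontinue |
| same, recovery in 8–14 days | hold, then 40 mg | discontinue |
| same, recovery in 15–28 days | hold, then 20 mg | discontinue |
| same, no recovery by day 28 | discontinue, or continue at the overall PI's discretion if clear benefit | discontinue |

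Apart from a stop for non-recovery without clear benefit, the two rows cannot both be followed.

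**Reading 2: the starred rows cover other non-hematologic toxicity, and the QTc rows cover QTc.** The QTc conflict disappears, but the starred rows then compete with Table 6-3's general rows.

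| Event | Table 6-8a, starred | Table 6-3 |
|---|---|---|
| Grade 3, recovery within 7 days | 60 mg | 40 mg |
| Grade 3, recovery in 8–14 days | 40 mg | 40 mg |
| Grade 3, recovery in 15–21 days | 20 mg | 40 mg |
| Grade 4 | may resume | discontinue |

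Over recovery days 1 to 21 the two tables give the same dose on 7 days (8–14) and different doses on 7 + 7 = 14. This counts rule entries and does not forecast how often they would apply. Recovery in 22–28 days is left out, because Table 6-3's answer there depends on when its 3-week limit starts to run.

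**Does other text settle Reading 1?** No. The ECG procedures describe a work-up and refer to the discontinuation criteria. The QT criteria in section 6.9 have no separate limit at 500 msec. The QTc row of Table 6-8a is the only place where more than 500 msec means stopping.

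**The case against.** The best defence is that the asterisk probably led to a note limiting the starred rows to toxicities other than QTc, and that this note may have been lost from the text. The table's structure supports this. The QTc rows form a complete scale of grades 1, 2 and ≥3; a separate QTc grade 1 row with no change would be redundant if the starred grade ≤2 row already covered QTc; and the starred text speaks of toxicity in general. On that view 510 msec has one action (discontinue) and 490 msec has one action (one level down). This is the likelier intention, and it stands as such. It does not close the point. The title places every row under QT prolongation, no visible text states the limit, and a limit to other non-hematologic toxicity leads to the contradictions with Table 6-3 under Reading 2. Notes to Tables 6-4, 6-5, 6-7 and 6-8 are visible, so loss of this one is possible but not shown.

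A reader might infer more than the documents support:
- *That the protocol plainly authorises re-dosing after QTc above 500 msec.* This depends on the scope of an asterisk whose note cannot be seen.
- *That the ECG procedures are a third, competing rule letting the investigator continue above 500 msec.* They are a work-up made subject to the discontinuation criteria, and an optional withdrawal list in section 6.9 does not cancel a mandatory stop in Table 6-8a. Section 6.9 has a gap; it does not contradict the table.
- *That the 28-day recovery window breaks the 21-day delay limit.* The follow-up text in section 6.7 counts delay from the intended day of the next injection, so a 28-day recovery need not exceed it.
- *That the grade 2 QTc row is unbounded because it joins its two limits with the word or.* The neighbouring rows fix the limits at 480 and 500 msec, so this is a slip.

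The protocol also excludes screening QTcF above 470 msec, prohibits QT-prolonging drugs and requires cardiology review above 480 msec. These reduce the risk but do not decide between the rows.

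**Conclusion.** The point holds as a defect of wording that matters for safety and should be corrected. On the visible text, one drug-related QTc above 500 msec can be read as hold and resume at 60, 40 or 20 mg, or as discontinue; a QTc above 480 and up to 500 msec can be read as no change or one level down. This assumes a patient starting at 60 mg and no asterisk note that limits the starred rows. If such a note limits them to other non-hematologic toxicity, the QTc conflict goes, but the dose conflict with Table 6-3 takes its place. Under either of these readings the text needs correction. No number of affected patients can be given, and sample size, power and error rates do not change.

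**What to change.** 1. State in Table 6-8a that the QTc rows alone govern QTc events. Confirmed QTcF above 500 msec means permanent discontinuation of pasireotide; above 480 and up to 500 msec means one dose level down. The word confirmed is essential: the ECG procedures require the cardiologist to re-evaluate the tracing first, and a misread ECG should not end treatment.
2. Add confirmed QTcF above 500 msec to the QT-related discontinuation criteria in section 6.9 as a stop in its own right.
3. Either restore the asterisk note with a scope and precedence consistent with Table 6-3, or delete the starred rows so that Table 6-3 governs other non-hematologic toxicity.

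The choice of clinical action rests with the sponsor's and investigators' clinicians. The cost is an amendment to wording, with no extra visits or patients. The one downside is less room for the investigator to continue a benefiting patient after a confirmed QTcF above 500 msec.

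### Safety rules conflict on QTcF above 500 msec, on the longest permitted treatment hold (28 against 21 days) and on the number of everolimus reductions (three against two)

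*Combined protocol and SAP*

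**What the plan says.** All places are in the combined protocol and SAP.

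**QT prolongation**
- *Section 6.7, ECG procedures.* A QTcF above 480 msec at any visit triggers a cardiology consultation. If the reading is confirmed, a cardiologist examines the patient. The patient stops if the investigator sees an acute risk. If instead "the investigator considers that there is not an acute cardiovascular safety risk and that the patient could continue to receive study medication", a 24-hour Holter ECG follows and the investigator makes the final decision. No dose change and no upper QTcF bound is given.
- *Section 6.7, Table 6-8a, QTc grade 2 row (above 480 to 500 msec).* The event counts "either drug related or drug unrelated". The patient is referred to cardiology, may stay in the study, and the "study drug dose will be reduced to 1 dose level down".
- *Section 6.7, Table 6-8a, QTc grade 3 or higher row (above 500 msec).* "Discontinue study drug Follow patient for safety".
- *Section 6.9, QT-related criteria.* The QTcF item is "Confirmed QTcF >480msec and discontinuation recommended by a cardiologist".

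**Hold limit**
- *Table 6-7* restarts study drug if hepatitis B reactivation resolves within 28 days.
- *Section 6.7, Follow-up for toxicities,* discontinues the patient once a dose is more than 21 days overdue.
- *Section 6.9* withdraws the patient after more than 21 days' delay for a treatment-emergent event. It keeps the period from 21 to 28 days for delays unrelated to treatment.
- *Table 6-8a, starred grade 3 or higher row,* resumes treatment after recovery in 15 to 28 days, and allows later continuation at the overall principal investigator's discretion.

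**Dose reductions**
- *Table 6-2* lists three steps below the starting dose for everolimus and two for pasireotide.
- *Section 6.9* begins: "Patients experiencing unacceptable toxicity (AE grade 3 or higher) that the investigator considers directly attributable to the study drug should have their dose adjusted", citing Table 6-2. It then allows no reduction beyond two levels and requires permanent discontinuation.

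**The concern.** Sites should be able to find one action for one finding. Here a site working from the ECG procedures could keep a patient with a confirmed QTcF above 500 msec on treatment, while a site working from Table 6-8a would stop. The trial is multicentre. Pasireotide is given in arms B and C and after crossover, and section 7.5.7 gives QT prolongation as the reason for repeat ECGs.

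The hold limit and the reduction count raise the same difficulty on a smaller scale: one text keeps on treatment a patient whom another withdraws. What is at stake is consistent safety management across sites, not the efficacy analysis.

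**Working it through.** The plan states no figure to reproduce. The check sets the texts side by side and uses arithmetic only to locate where the day limits collide.

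**1. QTcF.** Assumption: QTc in Table 6-8a means QTcF, the measure used in the ECG procedures.

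| Confirmed QTcF | ECG procedures, 6.7 | Table 6-8a, QTc rows | Section 6.9, QTcF item | Can all be followed? |
|---|---|---|---|---|
| 481-500 msec | Cardiology examination, then investigator's decision; silent on dose | Cardiology referral, may stay, one level down | Stop if the cardiologist so recommends | Yes: work-up plus dosing action |
| Above 500 msec | Same text, no upper bound; may continue | Discontinue | Same item, no 500 msec limit | No: discretion to continue against a required stop |

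The ECG procedures say that discontinuation criteria are to be followed but name no section. If section 6.9 is meant, its QTcF item brings in no 500 msec limit. The paragraph on day-21 visits goes further: where a Holter ECG is needed, it is timed to the next planned injection, with no exception above 500 msec.

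**2a. Hold limit, everolimus under Table 6-7.** The notes to Table 7-1 apply Table 6-7 to everolimus. Assumptions: the interruption starts with the 28-day count and, as dosing is daily, its length h equals the delay.
- Table 6-7 restarts for h = 1 to 28.
- The two 21-day rules withdraw for h > 21.
- Conflict: h = 22 to 28, which is 28 − 21 = 7 of 28 days.

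Reach is narrow, because section 7 makes patients with positive hepatitis B or C results ineligible.

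**2b. Hold limit, pasireotide under the starred row of Table 6-8a.** This is conditional on the row's scope. Injection is on day 1 and the next is due on day 29. Let the event be found on day d and recover t days later (t = 15 to 28, 14 values).
- Delay = d + t − 29. The 21-day rule applies if d + t − 29 > 21, that is, t > 50 − d.
- d = 22 or earlier: the maximum delay is 22 + 28 − 29 = 21, so 0 of 14 conflict.
- d = 23: t > 27, so 1 of 14.
- Each later day adds one.
- d = 29 (the planned injection day): t > 21, so 7 of 14.
- If t is instead counted from the planned injection day, 7 of 14 conflict whatever the value of d.

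The scheduled ECGs 21 days after the first and third injections fall on day 22 of the cycle, which gives 0 of 14 under the first count. The pre-injection ECG at cycle 6 falls on the planned injection day, which gives 7 of 14.

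**3. Reductions.**
- Everolimus: 3 levels in Table 6-2 against 2 in section 6.9. The texts conflict.
- Pasireotide: 2 against 2. The texts agree.
- Lowest dose: Table 6-7 restarts a patient already at the lowest dose at that same dose. Its footnote records hepatitis B reactivation as grade 3 (grade 4 if life-threatening). If the investigator attributes the event to study drug, section 6.9 permanently discontinues a patient already two levels down. These must also agree.

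**The case against.** The strongest reply is that the two QT texts do different jobs. One is headed as ECG procedures, and the other is a dose-modification table that follows directly. The grade 2 row repeats the cardiology referral, and the procedures twice refer to a first occurrence at a given dose level, which fits dosing action set elsewhere. This stands for 481-500 msec. A reader might infer that every reading above 480 msec draws contradictory instructions. The documents do not support that, because silence on dose is not an instruction to keep the dose.

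Above 500 msec, the reply is that the procedures only permit continuation, so a site that stops obeys both, and a specific table outranks a general procedure. That is a reasonable way to read it, but the protocol does not state it. The procedures give the investigator a decision that the table removes.

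Other tempting inferences also go too far:
- *Section 6.9 as a rival QT rule.* The withdrawal list that its QT criteria follow is permissive and does not bar stopping above 500 msec. It merely fails to supply the missing limit.
- *Unconfirmed readings as a conflict.* If the re-read does not confirm a value above 480 msec, there is no established grade 2 value for the table to act on.
- *The starred rows of Table 6-8a as a proven 28-against-21-day conflict.* Their footnote is not in the available text and may have been lost in extraction, and the start of the count is not given.
- *The third everolimus level as unusable.* Section 6.8 separately allows that schedule with moderate CYP3A4 or PgP inhibitors. The conflict concerns its use as a third reduction for toxicity under section 6.9.

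**Conclusion.** Three conflicts stand in the current text.

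1. Above 500 msec, a required stop in Table 6-8a meets discretion to continue in the ECG procedures, with no stated precedence. At 481-500 msec the only need is to say that the table sets the dosing action, or otherwise to state precedence.
2. Table 6-7 allows 28 days where two other texts allow 21. This is 7 of 28 days for daily everolimus, on the assumption that both counts start together, and it affects few patients. For pasireotide, any conflict with the starred row of Table 6-8a covers 0 to 7 of the 14 recovery days, depending on the day counted from and on a scope that cannot be judged here.
3. Table 6-2 lists three everolimus reductions where section 6.9 permits two, and the lowest-dose restart in Table 6-7 does not fit section 6.9.

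A reader might infer that these conflicts bias response rate or PFS. Nothing in the documents shows this, and it is not claimed.

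**What to change.** The clinical team should reconcile the passages or state which takes precedence:

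- **QT:** give one action for QTcF above 500 msec across the ECG procedures, Table 6-8a and section 6.9. State whether Table 6-8a sets the dosing action at 481-500 msec.
- **Starred rows of Table 6-8a:** confirm their scope and restore or confirm the footnotes.
- **Hold limit:** state one maximum and its start day, or an order of precedence, across Table 6-7, Table 6-8a, the follow-up text in section 6.7, and section 6.9.
- **Reductions:** make Table 6-2 and section 6.9 agree for everolimus, and make the lowest-dose restart in Table 6-7 agree with section 6.9.

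This review takes no view on which rule is right. The cost is a protocol amendment to tables and text, with the approvals that section 10.3 requires. It needs no extra patients or procedures.
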